9.2.5 Migraine Day

A migraine day is defined as a day of eDiary efficacy data with either (1) or (2):

- 1) Qualified migraine headache, defined as meeting both criteria a and b:
 - a. Headache lasting ≥ 30 minutes: "Yes" response to the question about lasting ≥ 30 minutes
 - b. Meeting ≥ 1 of the following criteria (i or ii):
 - i. ≥ 2 of the following pain features:
 - 1. Unilateral: "Yes" response to the question about unilateral
 - 2. Pulsating: "Yes" response to the question about pulsating
 - 3. Moderate or severe pain intensity
 - 4. Worsen or avoid physical activity: "Yes" response to the question about worsen or avoid physical activity
 - ii. ≥ 1 of the following associated symptoms:
 - 1. Nausea: "Yes" response to the question about nausea
 - 2. Vomiting: "Yes" response to the question about vomiting
 - 3. Both photophobia and phonophobia: "Yes" responses to the questions about photophobia and phonophobia
- 2) Acute migraine-specific medication day (see Section 9.2.4).

Migraine days are a subset of headache days (see Section 9.2.6).

If there are multiple sets of efficacy parameters on the same finding date, then data from all sets are used cumulatively to assess migraine day status on that day, regardless of finding time. Migraine pain intensity is set to the greatest pain intensity on that day.

A migraine day of total pain intensity is any migraine day, regardless of pain intensity.

9.2.6 Headache Day

A headache day is defined as a day of eDiary efficacy data with either (1), (2), or (3):

- 1) Migraine day (see Section 9.2.5)
- 2) Headache that lasts ≥ 30 minutes: "Yes" response to the question about lasting ≥ 30 minutes
- 3) Headache of any duration for which acute headache treatment is administered: Meeting both of the following criteria (a and b):
 - a) "Yes" response to the question about having a headache
 - b) "Yes" response to any of the 3 questions about taking medications to treat headache or aura (i.e., triptan, ergotamine, or other medications).

If there are multiple sets of efficacy parameters on the same finding date, then data from all sets are used cumulatively to assess headache day status on that day, regardless of finding time. Headache pain intensity is set to the greatest pain intensity on that day.

A headache day of total pain intensity is any headache day, regardless of pain intensity.

9.3 SAS Code

9.3.1 Linear Mixed Effects Model With Repeated Measures

Consider the following variables used to evaluate the primary efficacy endpoint using a linear mixed effects model with repeated measures:

- mdmchg: change from the OP in migraine days per month; continuous variable
- mdmop: migraine days per month during the OP; continuous variable
- month: month; categorical variable with levels of 1, 2, and 3
- rndstr: randomization stratum; categorical variable with levels of 1 and 2 to denote yes and no, respectively
- trt: treatment group; categorical variable with levels of 1, 2, and 3 to denote rimegepant EOD/placebo EOD, rimegepant QD, and placebo QD, respectively
- usubjid: unique subject identifier; categorical variable.

Then the SAS code is as follows:

proc mixed empirical; class usubjid rndstr trt month; model mdmchg = mdmop rndstr trt month trt*month; repeated month / subject=usubjid type=un; /* unstructured covariance */ lsmeans trt trt*month / alpha=0.025 cl diff; run;

9.3.2 Linear Regression Model

Consider the following variables used to evaluate the fifth secondary endpoint using a linear regression model:

- scorechg: score change from baseline at Week 12; continuous variable
- rndstr: randomization stratum; categorical variable with levels of 1 and 2 to denote yes and no, respectively
- scorebl: baseline score; continuous variable
- trt: treatment group; categorical variable with levels of 1, 2, and 3 to denote rimegepant EOD/placebo EOD, rimegepant QD, and placebo QD, respectively
- usubjid: unique subject identifier; categorical variable.

Then the SAS code is as follows:

proc mixed empirical; class usubjid rndstr trt; model scorechg = scorebl rndstr trt;

Pfizer Confidential

repeated / subject=usubjid; lsmeans trt / alpha=0.025 cl diff; run:

9.4 Study Drug Dosing Day

A study drug dosing day is defined as a day on which ≥ 1 tablet of study drug was taken.

For each subject, study drug dosing days and the number of tablets per day are determined for every day in the interval defined from the study drug start date to the study drug end date inclusive.

First, study medication records with complete study medication start date, complete imputed study medication end date, and number of tablets taken per day > 0 are selected. Imputed study medication end date, study drug start date, and study drug end date are derived (see Section 7.1).

Next, records are sorted by study medication start date, imputed study medication end date, wallet ID, and number of tablets taken per day.

Let [study medication start date1, imputed study medication end date1] and [study medication start date2, imputed study medication end date2] denote any 2 records.

Overlapping records are defined as maximum(study medication start date1; study medication start date2) \leq minimum(imputed study medication end date1; imputed study medication end date2). All days from the maximum to the minimum inclusive are considered overlapping study drug dosing days on which the number of tablets taken per day > 1. Note that overlapping records need not be consecutive.

Gaps between 2 consecutive records are defined as study medication start date 2 - imputed study medication end date $1 \ge 2$ days. All days from the imputed study drug end date 1 + 1 day to the study medication start date 2 - 1 day inclusive are considered days on which no study drug was taken (i.e., not study drug dosing days).

A DB study drug dosing day is defined as a day on which ≥ 1 tablet of DB study drug was taken. DB study drug dosing days are determined using valid DB wallet IDs.

An OL rimegepant dosing day is defined as a day on which ≥ 1 tablet of OL rimegepant study drug was taken. OL rimegepant dosing days are determined using valid OL wallet IDs.

Example:

Suppose study medication data are as follows for a given subject:

| Study Medication Start Date | Study Medication End Date | Imputed Study Medication End Date | Number of Tablets Taken per Day | Note |
|-----------------------------------|---------------------------------|---|---------------------------------------|------------------------------------|
| 01JAN2022 | 03JAN2022 | 03JAN2022 | 1 | |
| 04JAN2022 | 05JAN2022 | 05JAN2022 | 0 | Excluded from analysis |
| 06JAN2022 | 09JAN2022 | 09JAN2022 | 1 | |
| 09JAN2022 | 11JAN2022 | 11JAN2022 | 2 | 1-day overlap with previous record |
| 13JAN2022 | | 13JAN2022 | 1 | 1-day gap between previous record |

Then study drug start date = 01JAN2022 and study drug end date = 13JAN2022.

Study drug dosing days and number of tablets per day are derived as follows for the subject, taking overlaps and gaps into account:

| Date | Number of Tablets per Day | Study Drug Dosing Day Flag |
|-----------|---------------------------|----------------------------|
| 01JAN2022 | 1 | Y |
| 02JAN2022 | 1 | Y |
| 03JAN2022 | 1 | Y |
| 04JAN2022 | 0 | |
| 05JAN2022 | 0 | |
| 06JAN2022 | 1 | Y |
| 07JAN2022 | 1 | Y |
| 08JAN2022 | 1 | Y |
| 09JAN2022 | 3 | Y |
| 10JAN2022 | 2 | Y |
| 11JAN2022 | 2 | Y |
| 12JAN2022 | 0 | |
| 13JAN2022 | 1 | Y |

The subject has a total of 10 study drug dosing days and 14 tablets taken.

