 - O Migraine: subjects in the DBT efficacy analysis set with ≥ 14 days of eDiary efficacy data (not necessarily consecutive) in both the OP and ≥ 1 month (4-week interval) in the DBT Phase (see Section 6.3.1). This analysis set is used to assess migraine days, acute migraine-specific medication days, acute migraine medication days, and headache days.
 - o First month migraine: subjects in the DBT efficacy analysis set with ≥ 24 days of eDiary efficacy data (not necessarily consecutive) in both the OP and in first month (4-week interval) of the DBT Phase (see Section 6.3.3.3). This analysis set is used to assess efficacy endpoints per week.
 - o First week treated migraine: subjects in the DBT efficacy analysis set with (1) ≥ 24 days of eDiary efficacy data in the OP (not necessarily consecutive), (2) 7 consecutive days of eDiary efficacy data in the first week of the DBT Phase, and (3) 7 consecutive days of DB study drug dosing in the first week of the DBT Phase (see Section 6.3.3.5). This analysis set is used to assess efficacy endpoints per day.

See Section 7.1 for derived dates and Section 7.2 for analysis periods.

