By-subject LFT line plots are provided for the safety analysis set with select LFT elevations in any safety analysis period. Study weeks are defined as study day/7, where study day is derived from the laboratory test collection date (see Section 7.3). Each figure also displays DB study drug and OL rimegepant dosing days using symbols along the x-axis (see Section 9.4), and denotes additional study milestones (e.g., start of the on-DBT safety analysis period, start of the on-OL rimegepant safety analysis period, and start of the follow-up safety analysis period) using vertical lines with their corresponding descriptions in footnotes.

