7 CONVENTIONS

7.1 Derived Dates

Derived dates are defined as follows:

- eDiary efficacy date: complete datepart{eDiary finding date/time} 1 day
- Study drug start date: earliest complete study medication start date from IP Dosing CRF records with number of tablets taken per day > 0. This is an analysis period reference date.
- Imputed study medication end date: If the study medication end date is (1) noncomplete or (2) complete but before the study medication start date, then the imputed end date is set to the study medication start date. Otherwise, the imputed end date is set to the complete study medication end date. Derived only for IP Dosing CRF records with complete study medication start date and number of tablets taken per day > 0.
- Study drug end date: latest of (1) complete study medication start dates, or (2) complete study medication end dates from IP Dosing CRF records with number of tablets taken per day > 0
- Study drug last date:
 - Before the LSLV database lock: study drug end date derived only for subjects who have either (1) or (2):

- (1) "Yes" or "no" response to the phase completion question on the DB Subject Status CRF, and {either (1a) "no" response to the continuing to the next phase question on the DB Subject Status CRF, or (1b) "Follow-up" specified as the next phase on the DB Subject Status CRF}, and missing OL rimegepant start date
- (2) "Yes" or "no" response to the phase completion question on the OLE Subject Status or Follow-up Subject Status CRF
- o LSLV database lock: study drug end date

This is an analysis period reference date.

- DB study drug start date: earliest complete study medication start date from IP Dosing CRF records with number of tablets taken per day > 0 and valid DB wallet ID. This is an analysis period reference date.
- DB study drug end date: latest of (1) complete study medication start dates, or (2) complete study medication end dates from IP Dosing CRF records with number of tablets taken per day > 0 and valid DB wallet ID
- DB study drug last date:
 - Before all subjects have discontinued the DBT Phase: DB study drug end date derived only for subjects with "yes" or "no" response to the phase completion question on the DB Subject Status, OLE Subject Status, or Follow-up Subject Status CRF
 - o After all subjects have discontinued the DBT Phase: DB study drug end date

This is an analysis period reference date.

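### SAP 9.4's gap rule contradicts its own dosing-day definition when one dosing record lies strictly inside another, and can flag days with a recorded tablet as drug-free

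*SAP*

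**What the plan says.** SAP 9.4 opens with the definition: "A study drug dosing day is defined as a day on which ≥ 1 tablet of study drug was taken". It then gives a procedure. Records with zero tablets are dropped, end dates are imputed, and "records are sorted by study medication start date, imputed study medication end date, wallet ID, and number of tablets taken per day".

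Two rules follow, with different scope:

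- **Overlap rule.** Any two records are compared, and the days they share are marked as days with more than one tablet. The SAP adds: "Note that overlapping records need not be consecutive".
- **Gap rule.** Only neighbours in the sorted list are compared: "Gaps between 2 consecutive records are defined as study medication start date" of the second record minus the imputed end date of the first, when the difference is at least 2 days. The days from one day after the first record's end to one day before the second record's start "inclusive are considered days on which no study drug was taken (i.e., not study drug dosing days").

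On end dates, SAP 7.1 says that if the recorded end is incomplete or precedes the start, "then the imputed end date is set to the study medication start date".

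The dosing days derived this way are used in two places. In the by-subject liver function test (LFT) plots of SAP 6.4.2.2, "Each figure also displays DB study drug and OL rimegepant dosing days using symbols along the x-axis", with a reference to Section 9.4. The first week treated migraine set (SAP 4.1 and 6.3.3.5) requires "7 consecutive days of DB study drug dosing in the first week of the DBT Phase", and 6.3.3.5 again refers to Section 9.4.

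**The concern.** Comparing neighbours is enough only when no earlier record is still running past the end of the first record of the pair. Sorting by start date does not guarantee that. The overlap rule allows for non-neighbouring records, but the gap rule does not. The same section can therefore give two answers for one day: dosing day by the definition, drug-free day by the gap rule.

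The LFT plots are drawn only for subjects with select LFT elevations. Protocol 1.3 names liver test elevation as the primary identified adverse event of interest, so the timing of drug intake against the LFT values is the reason for showing dosing days there. A false break in the dosing symbols would mislead on exactly that. The second use is smaller: a subject with unbroken dosing in the first week could be left out of the set that serves exploratory objective 5.

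**Working it through.** **Inputs.** The definition, sort order, overlap rule, gap rule and worked example come from SAP 9.4. End-date imputation comes from SAP 7.1. The 8-tablet wallet comes from SAP 6.2.6.1. Days below are days in January.

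**Step 1: the SAP's own example.** After the zero-tablet record is dropped and the last end date imputed, the records are 1-3 (1 tablet a day), 6-9 (1), 9-11 (2) and 13-13 (1).

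- Neighbour differences: 6 - 3 = 3, so days 4 and 5 are gaps; 9 - 9 = 0, no gap; 13 - 11 = 2, so day 12 is a gap.
- Dosing days: 13 - 3 = 10.
- Tablets: 3×1 + 4×1 + 3×2 + 1×1 = 14.

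Both totals match the SAP. The end dates 3, 9, 11 and 13 rise throughout, so no record is nested and the example cannot reveal the conflict.

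**Step 2: a nested record.** Take 1-8, 3-3 and 9-16, each at 1 tablet a day. They sort in that order.

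- First pair: 3 - 8 = -5, no gap.
- Second pair: 9 - 3 = 6, which is at least 2, so days 4 to 8 are declared drug-free.
- The record 1-8 has a tablet on each of those 5 days. The overlap rule marks only day 3 and does not restore them.
- Result: 16 - 5 = 11 dosing days by the gap rule, against 16 by the definition.

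**Step 3: when it happens.** Two conditions are needed: the inner record starts later and ends earlier than the outer one, and the next sorted record starts at least 2 days after the inner record ends. With a single inner record,

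false days = min(outer end, next start - 1) - inner end.

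For an outer record on days 1-8 and a next record on day 9, this is 8 minus the inner end: from 1 day (inner end on day 7) to 6 days (inner record on day 2 only). There are no false days if the inner record shares the outer record's start or end, if no later record exists, or if records only partly overlap.

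**Step 4: imputation as a source.** Take 1-8, a record starting on day 7 with no end date, and 15-22. Section 7.1 makes the second record 7-7, which is now nested. The pair gives 15 - 7 = 8, so days 8 to 14 are declared drug-free, although day 8 is covered by the first record. That is 15 dosing days instead of 16.

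**Step 5: the corrected rule.** Measure each gap from the latest imputed end date among all earlier records. The SAP's example stays at 10 dosing days and 14 tablets. The Step 2 case gives 9 - 8 = 1, no gap, and 16 dosing days. Over 20,000 randomly generated record sets (2 to 6 records of 1 to 8 days each), the corrected rule agreed with the at-least-one-tablet definition every time. The rule as written produced false drug-free days in 2,607 sets, always with a strictly nested record present. These sets are synthetic and say nothing about how often this would occur in the trial.

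**The case against.** The best reply is that the opening definition governs. Section 9.4 says that dosing days and tablets are determined for every day from start to end, repeats the at-least-one-tablet test for double-blind and open-label drug, and shows an output table in which each day's tablet total drives the flag. A program built that way produces no false gap. This stands: the documents do not show the program, so the outcome is not fixed. But the SAP gives neither rule precedence, so two programmers could each follow the text and get different flags.

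The trigger is also narrow. The dosing form has a field for tablets per day, so an extra tablet need not create a second record. The protocol (7.4 and the footnotes to Table 1) has subjects finish one wallet before starting the next, so a nested record would usually reflect a dosing deviation. Still, SAP 6.2.6.2 plans for overlapping records, and Section 7.1 can create a nested one from a missing end date.

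A reader might infer three stronger claims that the documents do not support:

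- **That the liver plots will show false dechallenges.** This needs an LFT-elevation subject with qualifying records, a program that follows the gap sentence, and a reader who does not consult the study drug listing (SAP 6.2.6.1), which shows each record's dates, tablets and wallet.
- **That an extra-tablet day is an overdose followed by an apparent stop.** Protocol 8.3 treats an asymptomatic accidental second tablet as a deviation and reserves overdose for a dose that is both excessive and medically important.
- **That exposure or efficacy data are compromised.** Cumulative exposure and tablet-count compliance are summed over records, the more-than-one-tablet flag uses tablet counts and the overlap rule, and no primary or secondary efficacy analysis uses the gap rule.

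**Conclusion.** The contradiction within SAP 9.4 is certain on the text. Its effect is conditional and small. Under the two conditions in Step 3, and if the gap sentence is programmed literally, days covered by the outer record are flagged drug-free: 5 of 16 in the main example, and 1 to 6 for one inner record within a single 8-day wallet record when the next record starts on day 9 (assuming 1 tablet a day). The possible consequences are a false off-drug interval in an individual LFT plot and, only when the false gap falls in study days 1 to 7, wrongful exclusion from the first week treated migraine set. The documents give no frequency for such records, and none is assumed here. This is a minor flaw in a derivation rule, worth correcting because a stated rule gives a wrong answer and the SAP's example would not catch it.

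**What to change.** In SAP 9.4, replace the gap rule with: a day between study drug start and study drug end is a non-dosing day only if no selected record covers it. Equivalently, measure each gap from the latest imputed end date among all earlier records.

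Add a nested record to the worked example. For instance, one tablet on 07 JAN from a second wallet lies inside the 06-09 JAN record. The rule as written would then compare 9 - 7 = 2 and wrongly mark 08 JAN as drug-free, giving 13 - 4 = 9 dosing days. The correct answer stays at 10 dosing days, with 14 + 1 = 15 tablets.

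The cost is one sentence and one extra example row. If the program already counts tablets per day, it needs no change; otherwise only the gap step is affected. The SAP's present example keeps its stated results.
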